### 6. Study Methodology

The proposed study is a prospective, randomized controlled trial (RCT) that aims to compare the effectiveness of two topical treatments, HM Gel (Hydrophilic Methacrylate Gel) and BS Ointment (Beta Sitosterol Ointment), in promoting the healing process of episiotomy and cesarean section scars. The study will include two groups: an experimental group receiving HM Gel and a control group receiving BS Ointment.

**Sample size calculation or justification of numbers:** A priori sample size calculation will be conducted to determine the required number of participants for adequate statistical power. This calculation will consider factors such as the expected effect size, desired level of significance, power of the study, and anticipated dropout rate. We aim to recruit enough participants to ensure the statistical validity and generalizability of the study results.

The sample size for this study was determined based on the desired level of statistical power (80%) and the significance level (0.05). Since no prior estimates of effect size were available, a moderate effect size was assumed. Using a two-sample t-test, the sample size per group was calculated to be 53 participants in patients with cesarean section. Considering rounding up to the nearest whole number, a total sample size of

106 participants was determined for the 2 groups of cesarean section, and the same number for patients (53) with episiotomy, a total of 106 participants was determined for the 2 groups of vaginal delivery with episiotomy. This sample size calculation ensures that the study will have sufficient power to detect meaningful differences in pain levels and wound healing outcomes.

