### 7. Study Population and Study Setting/ Location

This study will be a prospective, randomized, controlled clinical trial. Participants will be randomly assigned to either an experimental group receiving HydrophilicMethacrylate Gel (HM Gel) or a control group receiving Beta Sitosterol Ointment(BS Ointment). The randomization process will utilize a stratified randomization method based on age and BMI to ensure balanced representation of different age groups and BMI categories within each treatment group.

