#### **Stratification:**

In our study, we will indeed have two distinct groups of patients: those who have undergone episiotomy and those who have undergone cesarean section. We recognize that the type of surgery is a potentially important factor that should be considered in the randomization process to ensure balanced representation of both surgical groups in each treatment arm. To address this concern, we will implement a stratified randomization approach that accounts for the type of surgery as a stratification factor. Specifically, during the randomization process, participants will be stratified into two groups: the episiotomy group and the cesarean section group. Within each of these strata, randomization will be performed independently to allocate participants to either the experimental group receiving Hydrophilic Methacrylate Gel (HM Gel) or the control group receiving Beta Sitosterol Ointment (BS Ointment). In our final study report, we will provide a detailed description of the randomization process, including how participants were allocated to treatment groups within each stratum.

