### Sample Size Calculation:

A sample size calculation has been performed to determine the required number of participants in each age and BMI stratum based on the expected effect size and statistical power.

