## 8. Study procedures

We plan to start the study as soon as MRC approval is obtained, and MRC approval letter is issued. The expected length of the study is one year.

Following MRC approval, we will start to stratify and recruit the patients based on inclusion

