### 10. Statistical Consideration and Data Analysis :

#### Randomization and Allocation Concealment:

We will be blinding the tube ointments to ensure impartiality in the assessment of efficacy between the two treatments. This adjustment will enable us to minimize potential biases and ensure the integrity of our results.

The ointment tubes will be packaged in identical outer packaging, such as opaque boxes, to conceal any distinguishing features.

This approach will ensure that the participants nor the assessors of wound know which ointment is being used. Blinding of data analysts will help ensure impartiality during the analysis process.

Randomization: We will indeed use computer-generated random numbers or randomization software to ensure unbiased and unpredictable allocation. Instead of stratifying during randomization, we will collect comprehensive data on age group, BMI, and type of surgery. Subgroup analyses will be conducted during data analysis, allowing for a thorough examination of treatment effects within specific subgroups.

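### The protocol both stratifies the randomisation and says it will not, and under the unstratified version surgery type enters neither the allocation nor the primary test

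*Combined protocol and SAP*

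**What the plan says.** All references are to the combined protocol and SAP.

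- **Section 7, opening paragraph:** "The randomization process will utilize a stratified randomization method based on age and BMI". Surgery type is not named, and no age or BMI cut-points are given.
- **Section 7, Stratification:** "we will implement a stratified randomization approach that accounts for the type of surgery as a stratification factor". There are two strata, episiotomy and caesarean section: "Within each of these strata, randomization will be performed independently to allocate participants". The final report is to describe allocation within each stratum.
- **Section 7, Sample Size Calculation:** a calculation is said to have been done to "determine the required number of participants in each age and BMI stratum". No numbers follow.
- **Section 8, Study procedures:** "Following MRC approval, we will start to stratify and recruit the patients based on inclusion" and exclusion criteria. The stratification factor is not named.
- **Section 10, Randomization and Allocation Concealment:** "Instead of stratifying during randomization, we will collect comprehensive data on age group, BMI, and type of surgery". Subgroup analyses are to follow. Allocation is computer-generated, with no ratio, blocking or minimisation stated.
- **Section 6, sample size:** 53 per arm, set separately for each surgery type: "106 participants was determined for the 2 groups of cesarean section, and the same number for patients (53) with episiotomy". A later paragraph raises recruitment to about 60 per group, and 10% dropout is anticipated.
- **Section 10, Primary Outcome Analysis:** healed versus not healed is compared between the two treatment groups by a chi-square or Fisher's exact test. Surgery type is not mentioned.

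**The concern.** The person who builds the allocation list needs one instruction. Here a reader of section 7 would build a stratified list and a reader of section 10 an unstratified one, and either list would depart from the protocol. The list has to be settled before the first patient is randomised and cannot be repaired afterwards.

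The factor at issue matters to this design. The trial pools perineal and abdominal wounds, is sized separately for each, and itself describes type of surgery as potentially important. If section 10 is followed, the mix of wounds in each arm is left to chance and the primary test does not allow for it. The subgroup analyses offered in place of stratification look at effects within subgroups and do not restore balance between arms. The later list of effect modifiers in section 10 gives age, BMI and parity as examples and does not repeat surgery type.

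**Working it through.** **1. Can the passages be reconciled?**

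| Place | Stratify? | Factor |
|---|---|---|
| Section 7, opening | Yes | Age, BMI |
| Section 7, Stratification | Yes | Surgery type, two strata |
| Section 8 | Yes | Not named |
| Section 10 | No | Age group, BMI and surgery type only recorded |

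The first two could be combined as surgery × age × BMI, although the Stratification paragraph as written has two strata only. Neither can be combined with the last row. All of this is current text, and nothing gives an order of precedence.

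**2. The plan's own sample size.** Inputs from section 6 are 80% power, significance level 0.05, a two-sample t-test and a moderate effect with no number. Sidedness is not stated.

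- Two-sided, standardised difference d = 0.55: 53 per arm by the t-test, which matches.
- Two-sided, d = 0.50: 64 per arm, which does not match.
- Dropout: 53 / (1 − 0.10) = 58.9, so 59, consistent with about 60.

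The effect size is therefore an assumption, and results below are given for d = 0.55, with d = 0.50 in brackets.

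**3. Chance imbalance in surgery mix without stratification.** Assumption: 60 per group means per arm within surgery type, so 60 × 2 × 2 = 240 patients, 120 per arm, half of them caesarean.

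- SD of the between-arm difference in caesarean share = √(2 × 0.25 / 120) = 0.0645, or 6.5 percentage points.
- P(difference beyond ±10 points) = P(|Z| > 0.10 / 0.0645) = P(|Z| > 1.55) = 0.12. Exact enumeration under simple randomisation gives 0.13.
- If overall arm totals were fixed at 120 each, the number of caesareans in one arm has SD 3.88. The difference in share then has SD 2 × 3.88 / 120 = 0.065, essentially the same.

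**4. Power within a surgery type** (two-sided t-test, 1:1 simple randomisation, averaged over the binomial split):

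| Patients of one type | Balanced arms | Unstratified, mean | 95% range for one arm |
|---|---|---|---|
| 106 | 80.1% (72.2%) | 79.7% (71.8%) | 43 to 63 |
| 120 | 84.8% (77.5%) | 84.5% (77.2%) | 49 to 71 |

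The average loss is 0.3 to 0.4 points. At the lower limit of the range it is 1.2 to 1.6 points.

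**The case against.** Several points can fairly be made on the other side.

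- **The documents do not contain three incompatible schemes.** A reader might count three. But the Stratification paragraph does not withdraw age and BMI, so the two stratified versions can be merged. The real conflict is two-way: stratify or do not. This stands.
- **Small arms are not a power shortfall.** A reader might note that, with 120 caesareans under simple randomisation, there is a 17% chance that one arm falls below 53 before dropout, and infer an underpowered comparison. That does not follow, because the other arm is correspondingly larger. A 52:68 split carries the information of 2 × 52 × 68 / 120 = 58.9 per arm. At d = 0.55 its power is 84.2%, against 84.8% at 60:60 and 80.1% at 53:53. The 17% also presumes simple randomisation, which section 10 does not specify. With arm totals fixed at 120 it is 5%.
- **Stratification does not deliver the planned numbers.** It balances arms within a surgery type but does not produce 106 or 120 patients of each type. That takes a recruitment target per type, which section 6 implies but does not operate. This stands, and the fix has to include it.
- **Unstratified randomisation is legitimate.** It gives an unbiased comparison, and with an adjusted analysis it would be a defensible design. This also stands. It does not rescue the present text, which promises both versions and specifies an unadjusted primary test.

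The claim that surgery type is the strongest prognostic factor is also not in the documents, which say only that it may be important.

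**Conclusion.** The concern holds as an unresolved contradiction in the allocation instructions. No single list can satisfy sections 7, 8 and 10, and the promised report of allocation within strata cannot be written if section 10 is followed. Under section 10, the factor on which the sample size is built is also left out of both the allocation and the primary test.

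The measurable consequence is avoidable imbalance in surgery mix: an SD of about 6.5 points in caesarean share, with about a 12% chance of more than 10 points. This rests on 240 patients split equally by surgery type and allocated 1:1. Both are readings of the plan, not statements in it.

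The documents do not support a claim of material power loss or of an invalid comparison. The reason to settle the matter before randomisation starts is that the design is not specified.

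**What to change.** State one scheme and use it everywhere:

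1. **Section 7, Stratification, and section 10:** computer-generated 1:1 allocation in permuted blocks, stratified by type of surgery only, with a separate list for each type. This is the scheme that fits the sample size in section 6.
2. **Recruitment:** add a target per surgery type that matches section 6 (106 needed, about 120 recruited, if 60 per group is meant per arm within type).
3. **Section 7, opening:** remove age and BMI as the basis of stratification. If they are kept, cut-points are needed and strata become small. With an assumed three categories of each, 3 × 3 × 2 = 18 strata would average 240 / 18 = 13 patients.
4. **Section 10:** delete the sentence that replaces stratification with data collection.
5. **Section 7, Sample Size Calculation, and section 8:** align both with the chosen scheme. Remove the reference to numbers per age and BMI stratum and name surgery type as the factor.
6. **Section 10, Primary Outcome Analysis:** analyse the primary outcome stratified by or adjusted for surgery type, for example with a Cochran-Mantel-Haenszel test or logistic regression. Age and BMI can be optional pre-specified covariates.

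The cost is wording changes, two lists instead of one and slightly more analysis work. No patients, visits or staff are added.

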#### Statistical Analysis Plan:

The statistical analysis plan will be as follows:

- **Descriptive Statistics:**  
Descriptive statistics will be used to summarize the demographic and baseline characteristics of the participants in both groups. Continuous variables, such as age and BMI, will be presented as means with standard deviations or medians with interquartile ranges, depending on their distribution. Categorical variables, such as parity and type of surgery, will be summarized as frequencies and percentages.
- **Primary Outcome Analysis:**  
The primary outcome of wound healing will be analyzed using appropriate statistical methods. As the wound healing outcome is likely to be a categorical variable (e.g., healed/not healed), we will employ the chi-square test or Fisher's exact test, depending on the expected cell frequencies, to compare the proportions of healed wounds.

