### Data Collection:

Data collection will involve objective measures and participant-reported outcomes. The assessment will include wound healing progress, scar appearance, pain levels, and patient satisfaction. These parameters will be assessed at predetermined intervals using standardized assessment tools and scoring systems.

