### Outcomes

- 1- The primary outcome of this trial is to assess the effectiveness of Hydrophilic Methacrylate Gel (Hemagel) in promoting wound healing and reducing complications in patients undergoing episiotomy or cesarean section procedures. Specifically, we aim to compare the rate and quality of wound healing between the group receiving Hemagel Ointment and the control group.
- 2- The secondary outcome includes evaluating the impact of Hydrophilic Methacrylate Gel on pain management, scar appearance, and patient satisfaction. We will assess pain levels using standardized pain scales and compare the effectiveness of Hemagel Ointment in alleviating pain compared to the control group. Additionally, scar appearance will be evaluated using validated assessment tools to determine if Hemagel Ointment leads to improved cosmetic outcomes. Patient satisfaction will be assessed through questionnaires to gauge the subjective experience and level of satisfaction with the treatment.

By achieving these objectives, this trial aims to provide evidence regarding the effectiveness of Hydrophilic Methacrylate Gel in promoting wound healing, managing pain, improving scar appearance, and enhancing patient satisfaction in the context of post-episiotomy and cesarean section scar.

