## HMC RESEARCH PROTOCOL

between the two treatment groups.

- **Secondary Outcome Analysis:**

For secondary outcomes, such as pain management, scar appearance, and patient satisfaction, we will use similar statistical methods. Pain management and patient satisfaction may be assessed using standardized pain scales and questionnaires, respectively. Depending on the distribution of the data, we will utilize t-tests or Mann-Whitney U tests to compare continuous variables and chi-square tests or Fisher's exact tests for categorical variables.

- **Intention-to-Treat (ITT) Analysis:**

The primary analysis will be conducted on an intention-to-treat (ITT) basis, including all randomized participants. This approach accounts for protocol deviations and maintains the randomization balance between the groups. Participants will be analyzed according to their allocated treatment group, irrespective of protocol adherence or completion.

- **Subgroup Analyses:**

We will perform subgroup analyses to explore potential effect modifiers, such as age, BMI, or parity, on the treatment outcomes. Interaction tests or stratified analyses may be employed to investigate the impact of these factors on the primary and secondary outcomes.

- **Statistical Software:**

All statistical analyses will be performed using a reputable statistical software package, such as SPSS or R. These software tools are widely used for data analysis and will provide reliable results for this study.

- **Statistical Significance:**

Statistical significance will be defined as a p-value less than 0.05. Results with p-values less than this threshold will be considered statistically significant, indicating a significant difference between the treatment groups.

- **Who Will Perform the Analysis:**

The data analysis will be carried out by qualified statisticians [name] (HMC biostatistician) with expertise in statistical methods. These individuals will be independent of the study's clinical team and will be blinded to the treatment allocation to ensure unbiased analysis.

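### The primary healing outcome, the t-test sizing and the chi-square test do not match, and no primary visit is named, so the stated 80% power does not apply to the planned test

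*Combined protocol and SAP*

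**What the plan says.** **Outcome.** Section 4 (Objectives) makes wound healing and fewer complications primary and refers to an attached validated tool. The Outcomes section narrows this: "we aim to compare the rate and quality of wound healing between the group receiving Hemagel Ointment and the control group". The Data Collection paragraph in section 7 adds: "These parameters will be assessed at predetermined intervals using standardized assessment tools and scoring systems". The follow-up visits are at Day 5 and Day 12 (section 6, details of the interventions).

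**Sizing.** Section 6 states: "The sample size for this study was determined based on the desired level of statistical power (80%) and the significance level (0.05"). On the effect it says only that "a moderate effect size was assumed". The method is clear: "Using a two-sample t-test, the sample size per group was calculated to be 53 participants in patients with cesarean section", with "the same number for patients (53) with episiotomy". The Sample Size Adjustment paragraph raises this to about 60 per group, after an allowance of 10% for dropout.

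**Test.** The Primary Outcome Analysis paragraph of the SAP says: "As the wound healing outcome is likely to be a categorical variable (e.g., healed/not healed"). It compares the proportions healed between the two arms by chi-square or Fisher's exact test. It does not say what counts as healed or at which visit, and it has no analysis of healing speed, healing quality or complications. On significance at 0.05 the SAP says: "Results with p-values less than this threshold will be considered statistically significant".

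**The concern.** The outcome, the sizing and the test describe three different things. A t-test sizing presumes a continuous measure, such as a score. A healed/not healed split of that score drops the grading within each category, which is the quality part of the stated outcome. It also reduces healing speed to the state at one moment. The 80% power claimed in section 6 is therefore not the power of the test in the SAP.

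The loss is greatest when most control wounds are already healed at the visit, because little room for improvement remains. Since no visit is named, that setting cannot be ruled out. The open visit also leaves more than one candidate primary result, each of which the significance rule would accept at 0.05. Blinding of the analysts does not remove that choice.

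**Working it through.** **Inputs from the documents.** Power 80%, alpha 0.05 (sidedness not stated), two-sample t-test, 53 per group in each surgery type, 10% dropout, about 60 recruited per group, visits at Day 5 and Day 12.

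**Assumptions, not in the documents.** Two-sided tests; standardised effect d = 0.50 or 0.55; control healing of 50% to 90%; healed/not healed is a cut of an underlying normal score. For pooling, the effect and the healed rate are taken to be the same in both surgery types.

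**1. The plan's own figure.** A two-sided t-test at 80% power needs 63.8, so 64 per group, for d = 0.50 and 52.9, so 53 per group, for d = 0.55. One-sided, d = 0.50 needs 51. The figure of 53 cannot be uniquely reproduced, because neither the effect nor the sidedness is given. I use d = 0.55 because it returns 53 and so gives the plan its claimed 80%. Dropout: 53/0.90 = 58.9, in line with about 60; 60 × 0.90 = 54 evaluable, so 53 is a fair working number.

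**2. Formula for the binary test.** With control proportion p1:

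- p2 = Φ(Φ⁻¹(p1) + d)
- power = Φ{[(p2 − p1)√n − 1.96·√(2p̄(1 − p̄))] / √[p1(1 − p1) + p2(1 − p2)]}, where p̄ = (p1 + p2)/2

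Example with p1 = 0.70 and d = 0.55: p2 = Φ(0.524 + 0.55) = 0.859, and the difference is 0.159. The two square-root terms are 0.5865 and 0.5756.

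- n = 53: (0.1587 × 7.280 − 1.96 × 0.5865)/0.5756 = 0.01, power 50%.
- n = 106: (0.1587 × 10.296 − 1.96 × 0.5865)/0.5756 = 0.84, power 80%.

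**3. Results.** Pooling gives 2 × 53 = 106 per arm.

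| Control healed | d = 0.55, n = 53 | d = 0.55, n = 106 | d = 0.50, n = 53 | d = 0.50, n = 106 |
|---|---|---|---|---|
| 50% | 60% | 88% | 52% | 82% |
| 70% | 50% | 80% | 44% | 73% |
| 80% | 41% | 70% | 36% | 63% |
| 90% | 28% | 49% | 24% | 44% |
| t-test on the score | 80% | 98% | 72% | 95% |

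Each column compares the two tests at the same sample size, so the gap to the last row is due to the change of test alone. At d = 0.50 and n = 53, the step from 80% to 72% comes from 53 being fewer than 64, not from the test.

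**4. Open visit.** If either of two visits could count as primary at 0.05, the false-positive rate is at most 1 − 0.95² = 9.75% under independence. With a correlation of 0.5 between the visits' test statistics (assumed) it is 9.1%, and with 0.9 it is 7.0%. Testing the surgery types separately as well would raise it further.

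**The case against.** The strongest reply is that the SAP compares the two arms and does not say that the primary test is run within each surgery type. The randomisation paragraph of section 10 places type of surgery under subgroup analyses. On that reading there are 106 per arm, and healed/not healed keeps 80% or more at d = 0.55 when control healing is 50% to 70%. This stands. A reader might infer that power falls well below 80% whatever happens, or that no improvement could be detected once 90% of controls are healed. The documents do not support either: both depend on testing within one surgery type and on an effect size and healed rates that the plan does not give. If a moderate effect is read as 0.5 on the arcsine scale for proportions, the binary test has 69% to 73% power at 53 per group for control healing of 80% to 50%, a modest shortfall.

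A reader might also infer that the trial would leave its question unanswered. That goes too far. A healed proportion answers part of the healing question, and the SAP's tentative wording leaves the variable open rather than fixing it as binary. That openness is itself the gap, however.

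A family-wise error near 18.5% could be computed for two visits by two surgery types. It rests on four independent tests that the SAP does not specify, so I do not rely on it.

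Finally, the healing tool is in an attachment not seen here. It may define healed, and it may or may not give a total score. The Day 5 and Day 12 visits are described in connection with adherence, so that healing is scored at both is a reasonable reading but not an explicit statement.

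**Conclusion.** The mismatch is in the text and does not depend on any assumption: the stated outcome, the sizing and the primary test are of different kinds, no primary visit is named, and complications have no primary analysis although they are in the primary objective. The 80% in section 6 does not describe the planned test.

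The size of the loss is conditional. At d = 0.55 and control healing of 50% to 90%, the binary test loses 20 to 52 percentage points against the t-test within one surgery type (80% down to 60% to 28%). Pooled, it loses 10 to 49 points (98% down to 88% to 49%). Pooled power is still adequate at control healing of 50% to 70% and falls short at 80% and above. The false-positive rate from an open choice between two visits is up to 9.75%, and less with correlated visits.

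**What to change.** 1. Name one primary variable and one visit: the total score of the attached wound-healing tool at, for example, Day 12.
2. Analyse it as one overall HM Gel minus BS Ointment difference with a 95% confidence interval, from a linear model adjusting for surgery type, and for baseline score if a usable one is recorded.
3. State that this analysis pools surgery types, and restate the power: about 95% to 98% at 106 per arm for d = 0.50 to 0.55. It agrees with the t-test sizing in type of outcome, but not in sample size, since section 6 sized each surgery type separately. Part of the gain over the per-type figures comes from pooling.
4. Make healed/not healed, the Day 5 score and the wound-complication proportion secondary, without primary significance claims.
5. Have the sponsor confirm that the tool gives a total score usable for both perineal and abdominal wounds, and that it is recorded at the chosen visit. If not, keep a binary primary with healed defined at one named visit, and restate the power or detectable difference at the planned size. For 80% power and control healing of 50% to 80%, that difference is 26 to 17 points at 53 per group, or 19 to 13 points at 106 per arm.

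The cost is wording in the outcome, sizing and SAP sections, provided the tool is scored as the protocol implies. It should be settled before any unblinding. The downside is that a mean score difference is less readable than a percentage healed, which stays as a secondary outcome.

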### **Details of the interventions (not procedures) involved in the research:**

The study involves the application of two topical treatments, HM Gel and BS Ointment, to the respective treatment groups. The application of these treatments will follow established protocols. The study does not involve any invasive procedures.

The administration of the assigned treatments will be administered in routine clinical practice following the surgical procedure, either episiotomy or cesarean section, and continue for a period of two weeks. During this period, the participants will be instructed on the proper application of the treatments. The application frequency and dosage will be as follows:

- Hydrophilic Methacrylate Gel (HM Gel): Participants in the experimental group will be instructed to apply HM Gel to the surgical site two times a day, in the morning and evening, for the duration of the two-week treatment period.
- Beta Sitosterol Ointment (BSO): Participants in the control group will be instructed to apply BSO to the surgical site two times a day, in the morning and evening, also for the duration of the two-week treatment period.
- The application process will be explained to each participant, emphasizing the importance of consistent and thorough application. Adherence to the treatment regimen will be monitored through regular follow-up visits. These follow-up visits will coincide with the baseline assessment, occurring at recruitment, and subsequent visits at Day 5 and Day 12 postpartum. The administration of the assigned treatments will commence immediately following the surgical procedure, either episiotomy or cesarean section, and continue for a period of two weeks. During this period, the participants will be instructed on the proper application of the treatments. The application frequency and dosage will be as follows:
  - Hydrophilic Methacrylate Gel (HM Gel): Participants in the experimental group will be instructed to apply HM Gel to the surgical site two times a day, in the morning and evening, for the duration of the two-week treatment period.

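### The primary and secondary tests use neither surgery type nor any baseline value; read as pooled tests, they lose power to the extent that surgery type predicts outcome.

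*Combined protocol and SAP*

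**What the plan says.** **Main tests (Section 10, Statistical Analysis Plan).** Healing is expected to be healed/not healed and is tested by chi-square or Fisher's exact test, "depending on the expected cell frequencies, to compare the proportions of healed wounds" between the two treatment groups. For secondary outcomes, "Depending on the distribution of the data, we will utilize t-tests or Mann-Whitney U tests to compare continuous variables", with chi-square or Fisher's test for categorical ones. No stratum term, covariate, model, effect estimate or confidence interval is named. Surgery type appears in the plan itself only as a descriptive baseline variable.

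**Subgroups.** The plan says "We will perform subgroup analyses to explore potential effect modifiers, such as age, BMI, or parity, on the treatment outcomes", and that interaction tests or stratified analyses may be used. The randomisation text earlier in Section 10 names surgery type together with age group and BMI as data to be collected for subgroup analysis.

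**Randomisation is described in three ways.**
- Section 7, opening paragraph: stratified by age and BMI.
- Section 7, Stratification: stratified by surgery type. "Within each of these strata, randomization will be performed independently to allocate participants" to the two arms.
- Section 10, Randomization and Allocation Concealment: no stratification at randomisation, with subgroup analyses instead.

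**Sizing and baseline.** Section 6 states "Using a two-sample t-test, the sample size per group was calculated to be 53 participants in patients with cesarean section", and the same number for episiotomy. On visits it says: "These follow-up visits will coincide with the baseline assessment, occurring at recruitment, and subsequent visits at Day 5 and Day 12 postpartum".

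**The concern.** Section 7 calls surgery type potentially important, and Section 6 gives each type its own sample size. The main tests carry neither decision through. A perineal wound and an abdominal wound may well heal at different rates by Day 5 or Day 12. If both go into one crude comparison, that difference is counted as noise.

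Three things are at stake:
- the power of the pooled comparison;
- if randomisation is stratified by surgery, the calibration of the test;
- a clear, prespecified result for each wound type, since the trial aims to inform care of both.

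In addition, choosing between the t-test and Mann-Whitney by looking at the data leaves open which treatment effect is being estimated.

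**Working it through.** **1. The plan's own figure.** Inputs from Section 6: 80% power, significance level 0.05, two-sample t-test, and "Since no prior estimates of effect size were available, a moderate effect size was assumed". The effect has no number, so 53 does not follow uniquely. A two-sided t-test at d = 0.5 needs 64 per arm, and 53 per arm then gives 72% power. A two-sided d of about 0.55 gives 53. With 10% dropout, 53/0.9 = 58.9, so 59, which fits the stated target of about 60. For the checks below, 60 × 0.9 = 54 evaluable per arm per surgery type, or 108 per arm pooled.

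**2. Standard error of a pooled chi-square under randomisation stratified by surgery.** With equal arms in each stratum, the arm difference varies only through within-stratum variance, while the chi-square test uses the pooled variance. For healing rates p1 and p2 (assumed; the documents give none):

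SE ratio = sqrt[ p̄(1 − p̄) / mean of p(1 − p) ], and true type I error = 2[1 − Φ(1.96 × ratio)].

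- 90%/50%: p̄ = 0.70; 0.210/0.170 = 1.235; ratio 1.11; type I error 2.9%.
- 85%/60%: p̄ = 0.725; 0.1994/0.1838 = 1.085; ratio 1.04; type I error 4.1%.
- Equal rates: ratio 1; type I error 5%.

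**3. Simulation.** 400,000 runs, 54 per arm per surgery type (on average, under simple randomisation), common odds ratio 2. The comparison is crude chi-square against Cochran-Mantel-Haenszel (CMH) stratified by surgery.

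| Control healing rates | Stratified: power, crude v CMH | Simple: power, crude v CMH | Crude type I error, stratified / simple |
|---|---|---|---|
| 75% / 75% | 51.6% v 51.2% | 51.1% v 50.8% | 5.1% / 5.0% |
| 80% / 70% | 50.6% v 50.8% | 50.3% v 50.4% | 5.0% / 5.0% |
| 85% / 60% | 50.0% v 52.3% | 49.6% v 51.8% | 4.2% / 5.1% |
| 90% / 50% | 44.7% v 51.3% | 44.8% v 51.0% | 3.0% / 5.1% |

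The type I error of CMH is 4.9% to 5.0% throughout. The power loss is almost the same under both forms of randomisation; the conservatism appears only under stratification by surgery. A more extreme case (60 per arm per surgery type, odds ratio 2.2, 30%/90%) gives 49.0% v 65.6%.

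**4. Continuous outcomes.** Assumptions: effect 0.3 within-surgery SD, surgery types differing by 1 SD, 108 per arm, stratified randomisation. Then 0.3/sqrt(2/108) = 2.205.

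- Unadjusted: the SE is inflated by sqrt(1 + 1/4) = 1.118; power = Φ(2.205 − 1.96 × 1.118) = 50.5%.
- Adjusted for surgery type: Φ(2.205 − 1.96) = 59.7%.
- Also adjusted for a baseline with correlation 0.5: Φ(2.205/sqrt(0.75) − 1.96) = 72.1%.

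About 9 of the 22 points come from surgery type, and about 12 from the assumed baseline correlation.

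**The case against.** **Pooling is inferred.** The plan never says that the surgeries are combined, and Section 6 sizes two separate pairs of groups. If separate tests within each surgery type were intended, omitting surgery type costs nothing. This stands as a limit on the point. The plan would then still have to say so, and say how two primary tests are handled.

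**The test may be valid.** A reader might infer that the standard errors and p-values are wrong because the trial is stratified. The documents do not settle that: Section 10 says there is no stratification, and under simple randomisation the crude test keeps its 5% level. Even under stratification by surgery the error is conservative, so there is no excess of false positives. Nor does the plan specify any confidence intervals that could be too wide.

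**Surgery-specific analysis is not absent.** A reader might infer that every comparison is unadjusted and that no result by surgery type is planned. Section 10 links subgroup analyses to surgery type, the later subgroup list is given as examples, and interaction or stratified analyses are allowed. These are optional and exploratory, however, and do not adjust the main tests.

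**Baselines may carry little.** Treatment is described as starting immediately after surgery, so a useful outcome baseline is plausible mainly for pain. The rise from 50.5% to 72.1% therefore does not apply to the primary outcome.

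**Conclusion.** The point holds in limited form. The primary and secondary tests use neither surgery type nor any baseline value. If they are pooled, power is lost to the extent that surgery type is prognostic, whichever randomisation text governs. At 54 per arm per surgery type and an odds ratio of 2, the loss is about 0 points with equal healing rates, 2 points at 85%/60% and 6 to 7 points at 90%/50%.

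The size rests on assumed rates, effects and correlations, since the documents give none, and the range starts at zero. The larger figures need a wide gap between the surgery types. A conservative test (type I error about 3% at 90%/50%) follows only if randomisation is stratified by surgery. A general claim of invalid inference is not supported.

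**What to change.** 1. Reconcile the three randomisation statements in Sections 7 and 10, and state that the primary analysis pools the surgeries with stratification by surgery type.
2. Healing: a Cochran-Mantel-Haenszel test with a common risk difference and 95% confidence interval, stratified by surgery type.
3. Continuous outcomes: a linear model with treatment, surgery type and the baseline value where one exists (mainly pain), replacing the data-dependent choice between t-test and Mann-Whitney.
4. Subgroups: add surgery type, already named in the randomisation text of Section 10, to the list in the Statistical Analysis Plan, with a treatment-by-surgery interaction test and a 95% confidence interval for the effect in each surgery type.

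**Cost:** revised wording and slightly more analysis work in SPSS or R, with no new data or patients. If surgery type turns out not to be prognostic, the stratified test gives up almost nothing (51.2% against 51.6% power at equal rates).
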